10. DATA ANALYSIS

The statistical analysis plan for the study is summarized below. This study will be descriptive in nature.

For continuous variables, they'll be descriptively summarized using the mean with the standard deviation (SD), the median with the interquartile range (IQR), and the maximum and minimum values, as appropriate.

For categorical variables, the numbers and proportions of patients in different categories of the variable will be reported. Missing values will be presented as counts and percentages but excluded from the denominator when calculating proportions, unless there are additional instructions specified.

For time-to-event variables, the number and percentage of patients with events and censoring

Statistical and Epidemiological Analysis Plan (SEAP) for Observational and Non-Interventional Studies (ONIS)

Page 17 of 36

will be summarized. The median survival time and its 95% confidence interval (CI) will be calculated using the Kaplan–Meier (KM) method, and KM plots will be provided.

It is anticipated that sample sizes for variables may vary due to unknown or missing data in the database. The number of patients with missing data for each variable will be summarized and reported. With the exception of the imputation of partial missing date values, no other imputation of missing values will be undertaken; however, the impact of missing data on interpretation of findings will be acknowledged and discussed in the final study report.

For all analyses, data for patients will be censored when lost to follow-up (i.e., still alive as of their last visit prior to end of study period).

10.1 MAIN ANALYSIS

10.1.1 Analysis of primary objective

OS will be analyzed for Cohort 1. For OS calculation, the event time is the date of death recorded by the National Mortality Database from CDC. OS is defined as the time from initiation of 1L until the date of death due to any cause. Patients without death record during the study period will be censored at the last medical record during the study period.

OS will be estimated by the KM method to obtain median estimates with 95% CIs and IQRs for Cohort 1, calculated using the log-log transformation. OS rate at 6, 12, 18, and 24 months will be described according to the survival curves if reached.

OS may be assessed by LOT and type of treatment received in each LOT, pending feasibility. OS by LOT is defined as the time from initiation of each LOT until the date of death due to any cause.

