9.3.1. Outcomes

9.3.1.1. Primary outcomes

OS

Outcome type: Primary

Outcome name: OS

• **Time frame:** Time from index date until the earliest record of death or end of the study period

Population: Cohort 1

OS as an event for each patient in Cohort 1 will be defined as the date of death minus the index date or the start day of each LOT. For patients with no record of death, OS will be censored at the last activity date before the end of the study period.

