9.7.5. Sensitivity analyses

Sensitivity analyses will be conducted:

- to only include patients in areas covered by the mortality surveillance system and with higher completeness on survival data.
- to only include patients before COVID-19 emergence (cohort identification period: January 1, 2013 December 31, 2019) to assess the possible impact of COVID-19 pandemic on treatment patterns and outcomes.

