9.9. LIMITATIONS OF THE RESEARCH METHODS

There are several limitations of this study. Firstly, CDC mortality surveillance data may only capture 80% of the total deaths, which may result in over-estimate of the survival outcomes. We attempt to conduct sensitivity analyses in area with higher completeness on survival data. Still, results should be interpreted with caution.

Secondly, the study could be subjected to missing clinical information that is not routinely recorded by clinicians, variations in the reporting, and selection biases arise from the use of diagnostic and therapeutic codes. Under-reporting of comorbidities and of treatment received outside the oncology clinic setting may result in misclassification of treatments and outcomes.

Additionally, as this study population includes patients from tertiary or oncology hospitals in China, study results might not be generalizable to entire Chinese DDLPS patients. As oncology care remain only possible or most optimally delivered though face-to-face, patients' access to oncological services is possibly limited during COVID-19 pandemic impacts, consequently resulting in less patient diagnosis and hospital visits.

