7.1 OUTCOMES

7.1.1 Primary outcomes

OS

Outcome type: PrimaryOutcome name: OS

• Time frame: Time from index date until the earliest record of death or end of the study

period

■ **Population:** Cohort 1

OS as an event for each patient in Cohort 1 will be defined as the date of death minus the index date or the start day of each line of therapy (LOT). For patients with no record of death, OS will be censored at the last activity date before the end of the study period.

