8. DATA SOURCES

will develop a custom, curated dataset for this study based on longitudinal electronic medical records (EMR) data from the NATDSS, the largest cancer registry database in China. This database, established in 2018 by China National Cancer Center (NCC), covers over 1400 hospitals across 31 provinces and over 10 million cancer patients in

Statistical and Epidemiological Analysis Plan (SEAP) for Observational and Non-Interventional Studies (ONIS)

Page 15 of 36

China. This multicenter hospital-based database consists of data of 1509 variables from 7 aspects including drug, patient basic information, inpatient, outpatient, tests and examinations, treatment and follow up. NATDSS is linked with National Mortality Database from Chinese Center for Disease Control and Prevention Center (China CDC) to obtain patients' death information [R23-1183].

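### Primary OS takes its event times from the CDC mortality database alone, so a death documented only in NATDSS would be censored and survival over-estimated

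*SAP*

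**What the plan says.** The operational rule for the primary outcome is in SAP 10.1.1: "For OS calculation, the event time is the date of death recorded by the National Mortality Database from CDC". The censoring rule follows in the same paragraph: "Patients without death record during the study period will be censored at the last medical record during the study period". It does not repeat whose death record is meant.

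The outcome definition is more general. Protocol 9.3.1.1 gives the time frame as "Time from index date until the earliest record of death or end of the study period", and SAP 7.1.1 words it the same way. Neither names a source of deaths.

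SAP 8 describes the database content and the linkage: "inpatient, outpatient, tests and examinations, treatment and follow up. NATDSS is linked with National Mortality Database from Chinese Center for Disease Control". Protocol 9.4 is nearly identical. Both give the linkage as the means of obtaining death information. Neither says whether NATDSS itself holds a death date or status.

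On completeness, Protocol 9.9 says: "CDC mortality surveillance data may only capture 80% of the total deaths, which may result in over-estimate of the survival outcomes". The visible response is a sensitivity analysis in Protocol 9.7.5: "to only include patients in areas covered by the mortality surveillance system and with higher completeness on survival data".

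**The concern.** OS is the only primary outcome. Protocol 7 says the survival data are meant to support a future New Drug Application; Protocol 12 adds that the study is not done solely for regulatory approval.

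Kaplan-Meier estimation assumes that a censored patient has the same later risk as those still under observation. A patient who has died but is missing from the CDC data breaks that assumption, because the last record tends to fall shortly before the death. Each such patient leaves the risk set without counting as an event, so the curve sits too high.

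Some of this cannot be helped: a death that no source records is lost. A death that the study's own database documents is different, because the rule would then set aside information already in hand. The area-restricted sensitivity analysis does not address this. It changes which patients are analysed, not how a death is ascertained.

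**Working it through.** **1. The plan's own figure.** Protocol 9.5 tabulates the 95% CI of the median OS, assuming exponential survival, medians of 8, 10 and 12 months and about 20% censoring. For N = 300 and a median of 10 it gives (8.408, 11.814). Without censoring, the Kaplan-Meier limits are approximately m × exp(±1.96 / (√N × ln 2)):

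10 × exp(±1.96 / (17.32 × 0.693)) = (8.49, 11.77)

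Simulation with 20% censoring and log-log limits reproduces all 12 rows within 1.4%. The table is right, so it can serve as a yardstick.

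**2. Closed form for missed deaths.** Let c be the share of deaths captured, independent of survival time, and suppose each missed death is censored at the time of death. The observed event hazard is then c × λ, and

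median read = ln 2 / (cλ) = m / c

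With c = 0.80 (Protocol 9.9), medians of 8 / 10 / 12 read as 10.0 / 12.5 / 15.0. The stated N = 300 upper limits are 9.435 / 11.814 / 14.198.

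The OS rates move the same way. True S(t) = 2^(−t/10) is read as 2^(−0.8t/10):

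| Month | True rate | Read at 80% capture |
|---|---|---|
| 6 | 66.0% | 71.7% |
| 12 | 43.5% | 51.4% |
| 18 | 28.7% | 36.9% |
| 24 | 18.9% | 26.4% |

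**3. Allowing a gap between last record and death.** The documents do not give this gap, so it is an assumption. Potential follow-up runs uniformly from 12 to 120 months (index January 2013 to December 2021, study end December 2022). Each scenario has 1,000,000 simulated patients, 80% capture and a true median of 10. Ranges cover censoring survivors at their last record or at study end.

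| Gap, last record to death | Median read (months) |
|---|---|
| None | 12.5 |
| Mean 3 months | 12.0 to 12.1 |
| Mean 6 months | 11.6 to 11.8 |
| Last visit uniform over follow-up | 11.2 to 11.6 |

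The first two rows exceed 11.814; the last two do not. Across medians 8, 10 and 12 the over-estimate is about 11% to 25%. With a falling hazard (Weibull shape 0.8) it is 14.5% to 32%; with a rising hazard (shape 1.2) it is 8.5% to 20%.

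**4. What a change of rule could recover.** If NATDSS records a share r of the CDC-missed deaths, capture becomes 0.8 + 0.2r. True median 10, same follow-up:

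| r | Capture | No gap | 3-month gap | Uniform last visit |
|---|---|---|---|---|
| 0 | 0.80 | 12.5 | 12.0 | 11.2 to 11.6 |
| 0.5 | 0.90 | 11.1 | 10.9 | 10.4 to 10.7 |
| 1 | 1.00 | 10.0 | 10.0 | 9.8 to 10.0 |

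The documents do not give r.

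**The case against.** The best defence is that the rule is clear and deliberate. SAP 10.1.1 names one source, the death record in its censoring sentence most naturally means that source, and the data-source sections present the linkage as the way to obtain deaths. Sections 7.1.1 and 9.3.1.1 then give the general definition and 10.1.1 the operational one. This stands. A reader might infer that the sections contradict each other, or that the SAP has no rule for a NATDSS-only death; the text supports neither reading. A reader might also take the earliest record of death to imply several death sources. It reads as readily as the earlier of two endpoints, death or study end. SAP 10 describes patients as "censored when lost to follow-up (i.e., still alive as of their last visit prior to end of study period", which fits poorly with someone recorded as dead, but it is a gloss on loss to follow-up and not a competing rule.

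It also stands that no visible text confirms death status in NATDSS. The variable list and the data management plan are separate documents, and the SAP text between 10.1.2 and 10.3 cannot be seen. The protocol discloses both the under-capture and its direction.

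Finally, counting more deaths does not bring the estimate closer to the truth in every scenario. With an assumed 12 to 36 months of follow-up and everyone without a captured death censored at a uniformly placed last visit, a true median of 10 reads 10.42 at 80% capture and 9.17 at full capture. That shows a second bias, from censoring survivors at their last visit, partly cancelling the first. It is no reason to leave out known deaths.

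**Conclusion.** The point holds as a weakness in a stated rule. Followed as written, SAP 10.1.1 would censor a death documented only in NATDSS, and that biases OS upward. At the protocol's own 80% capture figure, the total under-capture bias on a 10-month median is about 1.2 to 2.5 months. This assumes exponential survival, deaths missed at random and 12 to 120 months of follow-up. It is an illustration, not a bound: with the shorter assumed follow-up of 12 to 36 months, the net error across medians 8, 10 and 12 runs from about −1% to +25%.

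A reader might infer that the fix would remove the whole 11% to 25%, or that the plan is known to discard recorded deaths. The documents support neither. The recoverable part depends on how many CDC-missed deaths NATDSS holds, possibly none. No stated figure is wrong. The change is worth making because it is cheap, concerns the sole primary outcome, and addresses an error that the confidence interval will not show.

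**What to change.** In SAP 10.1.1, define the OS event as a death recorded in the CDC linkage or in NATDSS inpatient or follow-up data, where these hold death status. State which date prevails when the two differ, and apply the partial-date rule of SAP 9.4 (a missing day becomes the 15th) to death dates. Report the number of deaths by source: CDC only, NATDSS only, both. Keep the CDC-only definition as a sensitivity analysis. Use the same definition in SAP 7.1.1 and Protocol 9.3.1.1.

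If NATDSS holds no death status, say that CDC is the sole source and align 7.1.1 and 9.3.1.1 with 10.1.1. The estimate then does not change.

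The cost is one source variable, a date-conflict rule and a little programming.

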10.1.2 Analysis of secondary objectives

Survival after initial diagnosis will be estimated by the KM method to obtain median estimates with 95% CIs and IORs for Cohort 1 and Cohort 2.

Treatment patterns for Cohort 1 and Cohort 2 will be described by the number of lines, count with percentage (%) of patients by treatment lines, type of therapy and therapy regimens in each line.

LOTs are defined by the temporal relationship and sequencing of treatment regimens by using the dates of initiation and discontinuation of chemotherapy, targeted therapy, and/or immunotherapy. For each patient, 1L treatment regimen is defined as the first systemic treatment of any chemotherapy, and/or targeted drugs given to a patient after advanced or metastatic DDLPS diagnosis. A treatment line is advanced to the next line when a patient initiates new combinations of drugs or has the evidence of progression of disease. The start date of each LOT is defined as the date of initiation of new regimen, and the end date of each LOT is defined as the date of last dose prescribed or recorded at/before discontinuation.

Statistical and Epidemiological Analysis Plan (SEAP) for Observational and Non-Interventional Studies (ONIS)

Page 18 of 36

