9.5. STUDY SIZE

The patient sample was a convenience population of all eligible patients in the database who met inclusion and exclusion criteria during the study period; no priori power analyses were conducted.

NIS Protocol BI Study Number 1403-0024 Page 22 of 37 C42272174

Proprietary confidential information© 2023 Boehringer Ingelheim GmbH or one or more of its affiliated companies

A preliminary feasibility check will be conducted to assess potential eligible sample size as below.

Criteria
Patients with at least one diagnosis of DDLPS
Patients aged 18 years old or above at initial diagnosis
Patients have two or more documented clinical visits between January 1, 2013 and December 31, 2022

We estimated the precision we can expect from the estimates of a median OS for different potential sample sizes. It is assumed that the enrollment rates follow uniform distribution in the study period and that the survival time follows exponential distribution with median OS=8, 10, and 12 months. The censor rate is approximately 20% with type I of right censoring. The 95% CI of median OS is shown in the below table under different scenarios.

N (Sample Size)	Median Overall Survival from start of 1L, Months	95% CI of Median Overall Survival
1500	8	(7.419, 8.625)
1000	8	(7.287, 8.764)
500	8	(7.011, 9.095)
300	8	(6.732, 9.435)
1500	10	(9.262, 10.784)
1000	10	(9.100, 10.972)
500	10	(8.754, 11.378)
300	10	(8.408, 11.814)
1500	12	(11.110, 12.948)
1000	12	(10.916, 13.175)
500	12	(10.491, 13.677)
300	12	(10.073, 14.198)

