9.7.3. Analysis of exploratory objectives

Patient demographic, clinical characteristics and treatment outcomes will be reported for Cohort 1 and Cohort 2 (See Section 9.3.1.3 for variable definitions). If multiple records for a variable exist during the baseline period, the record closest to index will be chosen. The number of missing values will be reported for each variable, and percentages for categorical variables will be based on non-missing values. Time from diagnosis to 1L treatment, time to next treatment and duration of treatment by LOT will be estimated using KM methods to obtain median estimates with 95% CIs and IQRs.

HCRU including number of visits and days of hospitalization will be summarized as counts (n) and proportions (%). Direct medical cost will be summarized using mean, median and IQR.

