6.4 STUDY VISITS

Definitions of relevant time periods are detailed below.

Study period: January 1, 2013 – December 31, 2022

Baseline period: All available data prior to index date

Cohort identification period: January 1, 2013 – December 31, 2021 (one year before end of study period)

[figure not shown]
Statistical and Epidemiological Analysis Plan (SEAP) for Observational and Non-Interventional Studies (ONIS)

Index date: The index date for Cohort 1 will set to the date of initiation of 1L treatment; the index date for Cohort 2 will be the date of initial DDLPS diagnosis during cohort identification period.

Follow-up period: From index date until date of death, if available, or the date of censoring if there is no record of death, whichever occurs first. For survival and treatment patterns, the date of censoring will be the last activity date, defined as the date of the last visit of any type prior to the end of the study period.

Figure 1 illustrates the time periods for the study timelines.

(a). Cohort 1

(b). Cohort 2

[figure not shown]

Figure 1. Overall study period

Abbreviations: 1L = first line

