7.1.2 Secondary outcomes

Survival after initial diagnosis

Outcome type: Secondary

• Outcome name: Survival after initial diagnosis

• **Time frame**: Time from initial diagnosis until the earliest record of death or end of the study period

• **Population**: Cohort 1, Cohort 2

Survival after initial diagnosis for each patient will be defined as the date of death minus the date of initial diagnosis. For patients with no record of death, survival after initial diagnosis will be censored at the last activity date before the end of the study period.

Description of treatment patterns

Outcome type: Secondary

• Outcome name: Treatment patterns

• Time frame: Treatment patterns are assessed at the index date and during follow-up

■ **Population**: Cohort 1, Cohort 2

The following variables of interest will be assessed to describe treatment patterns defined by LOT and regimens.

Treatment patterns by LOT and regimens

Variable	Definition	Timing
1L Treatment Type	Regimen name from LOT data for treatments with line number = 1, 2 and 3. Treatment	Any time after
2L Treatment Type	types will be classified as follows, specific treatments and categories may change upon examination of the data:	index date
3L Treatment Type		

Statistical and Epidemiological Analysis Plan (SEAP) for Observational and Non-Interventional Studies (ONIS)

[figure not shown]
Variable	Definition	Timing
	NCCN/CSCO preferred	
	 Doxorubicin 	
	 Epirubicin 	
	 Liposomal doxorubicin 	
	AD (doxorubicin, dacarbazine)	
	 AIM (doxorubicin, ifosfamide, mesna) 	
	Ifosfamide, epirubicin, mesna	
	 Larotrectinib (NTRK fusion pos sarcomas only) 	
	 Entrectinib (NTRK fusion pos sarcomas only) 	
	 Pazopanib 	
	• Eribulin	
	Trabectedin	
	Other	
	 AD LMS only (doxorubicin, dacarbazine) 	
	Gemcitabine and docetaxel	
	Gemcitabine	
	Gemcitabine and vinorelbine	
	Gemcitabine and dacarbazine	
	 Dacarbazine 	
	 Ifosfamide 	
	Temozolomide	
	Vinorelbine	
	 Regorafenib 	
	 MAID (mesna, doxorubicin, ifosfamide, dacarbazine) 	
	 Pembrolizumab 	
	 durvalumab 	
	• Other	
Total number of treatment lines	From LOT data, for all lines after index date, categorical variable defined as total of treatment lines reported.	Any time after index date
Concurrent steroid therapy	Any record of a drug classified as a corticosteroid.	Anytime from the start to end of 1L, 2L, or 3L

Statistical and Epidemiological Analysis Plan (SEAP) for Observational and Non-Interventional Studies (ONIS)

Page 9 of 36

Variable	Definition	Timing

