Clinical characteristics	Cohort 1	Cohort 2
Primary tumor site, N (%)		
Head or neck		
Retroperitoneum or abdomen		
Extremity		
Pelvis		
Thorax or trunk		
Other		
Missing / Unknown		
Presence of metastases, N (%)		
Yes		
No		
Missing / Unknown		
Metastatic site, N (%)		
Adrenal		
Bone		
Brain		
Distant lymph node metastases		
Liver		
Lung		
Other		
Missing / Unknown		
Number of surgeries prior to 1L		
$Mean \pm SD$		
Median (IQR)		
Min, Max		
Missing / Unknown		
Charlson comorbidity index		
$Mean \pm SD$		
Median (IQR)		
Min, Max		
Missing / Unknown		
History of smoking, N (%)		

Statistical and Epidemiological Analysis Plan (SEAP) for Observational and Non-Interventional Studies (ONIS)

Page 24 of 36

Clinical characteristics	Cohort 1	Cohort 2
Never smoker		
Former smoker		
Current smoker		
Missing / Unknown		
$BMI, kg/m^2$		
$Mean \pm SD$		
Median (IQR)		
Min, Max		
Missing / Unknown		

Abbreviations: N = number; SD = standard deviation; IQR = interquartile range; min = minimum; max = maximum; BMI = body mass index (defined as [weight in kilograms] / [height in meters]²); ECOG = Eastern Cooperative Oncology Group; 1L = first line.

Statistical and Epidemiological Analysis Plan (SEAP) for Observational and Non-Interventional Studies (ONIS)

Page 25 of 36

Table 3. Overall survival from index for Cohort 1

At 18 months, [95% CI]

At 24 months, [95% CI]

	Cohort 1	
	N=	
Overall survival from Index, months		
KM Median, [95% CI]		
IQR		
Survival rate at different time point, (100/1000 person years) At 6 months, [95% CI]		
At 12 months, [95% CI]		

Abbreviations: KM= Kaplan–Meier; CI = confidence interval; IQR = interquartile range.

Statistical and Epidemiological Analysis Plan (SEAP) for Observational and Non-Interventional Studies (ONIS)

Page 26 of 36

Table 4. Survival from initial diagnosis for Cohort 1 and Cohort 2

	Cohort 1,	Cohort 2,	
	N =	N=	
Survival from initial diagnosis, months			
KM Median, [95% CI]			
IQR			
Survival rate at different time point, (100/1000 person years) At 6 months, [95% CI]			
At 12 months, [95% CI]			
At 18 months, [95% CI]			
At 24 months, [95% CI]			

Abbreviations: KM= Kaplan–Meier; CI = confidence interval; IQR = interquartile range.

Statistical and Epidemiological Analysis Plan (SEAP) for Observational and Non-Interventional Studies (ONIS)

Page 27 of 36

Table 5.	Number	of total	lines of	f systemic	treatment

	Cohort 1,	Cohort 2,
	N=	N=
Total lines of systemic treatment		
$Mean \pm SD$		
Median (IQR)		
Min, Max		

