Missing / Unknown		
Total lines of treatment (categorized), N (%)		
1		
2		
3		
4		
≥5		
Missing / Unknown		

Abbreviations: N = number; SD = standard deviation; IQR = interquartile range; min = minimum; max = maximum.

Statistical and Epidemiological Analysis Plan (SEAP) for Observational and Non-Interventional Studies (ONIS) Page 28 of 36

Table 6. Treatment types for Cohort 1 and Cohort 2 by line of therapy

V 1	Cohort 1,				Cohort 2,		
	N=				N =		
	1L	2L	3L	_	1L	2L	3L

Treated, N (%)

Yes

No

Regimens, N (%)

Doxorubicin

Epirubicin

Liposomal doxorubicin

AD (doxorubicin, dacarbazine)

AIM (doxorubicin, ifosfamide, mesna)

Ifosfamide, epirubicin, mesna

Larotrectinib (NTRK fusion pos sarcomas only)

Entrectinib (NTRK fusion pos sarcomas only)

Pazopanib

Eribulin

Trabectedin

AD LMS only (doxorubicin, dacarbazine)

Gemcitabine and docetaxel

Gemcitabine

Gemcitabine and vinorelbine

Gemcitabine and dacarbazine

Dacarbazine

Ifosfamide

Temozolomide

Vinorelbine

Regorafenib

MAID (mesna, doxorubicin, ifosfamide, dacarbazine)

Statistical and Epidemiological Analysis Plan (SEAP) for Observational and Non-Interventional Studies (ONIS)

Page 29 of 36

	Cohort 1,			Cohort 2,			
		N =			N=		
·	1L 2L 3L		1L	2L	3L		

Pembrolizumab

durvalumab

Other

Concurrent steroid therapy, N (%)

Yes

No

Concurrent immunosuppressant therapy, N (%)

Yes

No

Concurrent hormone replacement therapy, N (%)

Yes

No

Abbreviations: 1L = first line; 2L = second line; 3L = third line.

Notes: Specific treatments and categories are ordered from highest to lowest frequency and may change upon examination of the data.

Statistical and Epidemiological Analysis Plan (SEAP) for Observational and Non-Interventional Studies (ONIS)

Page 30 of 36

Table 7. Time to next treatment	by l	line of	f treatment f	for	Cohort 1	and	Cohort 2
---------------------------------	------	---------	---------------	-----	----------	-----	----------

	Cohort 1,	Cohort 2,
	N =	N=
Treated, N (%)		
Yes		
No		
Time from diagnosis to 1L treatment, months Median, [95% CI]		
IQR		
Fime from 1L treatment to 2L treatment, months Median, [95% CI]		
IQR		
Time from 2L treatment to 3L treatment, months Median, [95% CI]		
IQR		

Abbreviations: CI = confidence interval; IQR = interquartile range; 1L = first line; 2L = second line; 3L = third

Statistical and Epidemiological Analysis Plan (SEAP) for Observational and Non-Interventional Studies (ONIS)

Page 31 of 36

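### Tables 5 and 6 give raw line counts although treatment patterns have a censoring date, so patients censored on a line are merged with those who died and eventual 2L and 3L use is understated

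*SAP*

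**What the plan says.** On censoring, SAP 6.4 states: "For survival and treatment patterns, the date of censoring will be the last activity date". It defines that date as the last visit of any type before the end of the study period. SAP 10 adds: "For all analyses, data for patients will be censored when lost to follow-up". Protocol 9.2.3 and 9.7 say the same.

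On analysis, SAP 10.1.2 says that treatment patterns in both cohorts "will be described by the number of lines, count with percentage (%) of patients by treatment lines", with therapy type and regimen in each line. SAP 7.1.2 defines the number of lines thus: "From LOT data, for all lines after index date, categorical variable defined as total of treatment lines reported".

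In SAP Annex 2, Table 5 ("Total lines of systemic treatment") gives mean, median and categories, with a row for missing or unknown values. Table 6 gives Treated Yes or No under 1L, 2L and 3L for each cohort. Those Treated rows have no category for a patient whose follow-up ended during the previous line.

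Some line transitions do get a time-to-event analysis, as exploratory outcomes. Protocol 9.7.3 says: "Time from diagnosis to 1L treatment, time to next treatment and duration of treatment by LOT will be estimated using KM methods". The matching shell, Table 7, has rows such as "Time from 2L treatment to 3L treatment, months" with a median, confidence interval and interquartile range.

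**The concern.** A No under 2L in Table 6 can mean three things: the patient died on 1L, was still on 1L at the end of the study period, or was lost from the network alive. Only the first is a settled No. The visible text does not say how the other two are classified. Nor does it say whether they count as missing, which SAP 10 would take out of the denominator. Two programmers could reach different 2L percentages for a secondary objective.

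If all three are counted as No, the percentage depends on length of follow-up as well as on practice. That matters when groups with unequal follow-up are compared. Annex 2 replicates the shells for subgroups and sensitivity analyses where feasible. Year of initial diagnosis is a possible subgroup (Protocol 9.7.4), the pre-COVID sensitivity analysis is aimed at treatment patterns among other outcomes (Protocol 9.7.5), and Tables 5 and 6 set Cohort 2 beside Cohort 1. A shorter window could be read as a change in practice.

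**Working it through.** **The plan's own figure.** The documents give no figure for line use. The only censoring share is in Protocol 9.5: "The censor rate is approximately 20% with type I of right censoring". It belongs to the precision table for median OS. A simulation with exponential survival, uniform censoring tuned to 20% and log-log intervals for the Kaplan-Meier median matches all 12 rows within 0.7%. For N = 500 and a median of 10 months it gives 8.76 to 11.45, against 8.754 to 11.378 in the protocol. So the 20% is a usable input, but as a share of patients censored for OS.

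**Inputs.** Median OS 8, 10 and 12 months (Protocol 9.5). Median progression-free survival 2 to 4 months (Protocol 7), used as a rough stand-in for time on a line; this is an assumption. Hazards are assumed constant and the same on each line: *a* for starting the next line, *d* for death, *c* for loss.

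**Formulas.**
- *d* = ln 2 / median OS, and *a* + *d* = ln 2 / median time on a line.
- True share reaching 2L: T = *a*/(*a*+*d*).
- OS censoring share s = *c*/(*c*+*d*), so *c* = *d*·s/(1−s).
- Raw share reaching 2L: *a*/(*a*+*d*+*c*) = T / [1 + (1−T)·s/(1−s)].
- For 3L, square each share.

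**Results at s = 20%,** three of the nine combinations:

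| Median OS / time on line (months) | 2L true → raw | 3L true → raw |
|---|---|---|
| 8 / 4 | 50.0% → 44.4% | 25.0% → 19.8% |
| 10 / 3 | 70.0% → 65.1% | 49.0% → 42.4% |
| 12 / 2 | 83.3% → 80.0% | 69.4% → 64.0% |

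Over all nine, the shortfall is 3.3 to 5.6 points for 2L and 5.2 to 6.6 for 3L. At an assumed 40% censoring it is 8 to 13 and 11 to 15. At an assumed true 2L share of only 30% and 20% censoring, 2L falls from 30.0% to 25.5% and 3L from 9.0% to 6.5%.

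**Cut-off at study end alone, with no loss.** Write x = ln 2 × months / median time on a line. By x, the fraction of eventual 2L starts seen is 1 − e^(−x), and of eventual 3L starts 1 − e^(−x)(1+x).
- Cohort 1, index spread evenly over 2021 (12 to 24 months available): 95% to over 99% of eventual 2L use and 80% to 98% of eventual 3L use, for median time on a line of 4 and 2 months.
- Cohort 1, index by the end of 2019 (at least 36 months): at 4 months per line, x = 9 × 0.693 = 6.24, so at least 98.6% of eventual 3L use.
- Cohort 2, 1L starts spread evenly over 2022 (0 to 12 months): 58% to 76% of eventual 2L use and 28% to 54% of eventual 3L use among those who start 1L.

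**Which estimator recovers the share.** One case was simulated with N = 500, 1,000 replicates, median OS 10 months, true 2L share 50% and 20% OS censoring. The raw share was 44.5% and the Aalen-Johansen estimate 50.0%. At 24 months the true value was 48.2%, raw 43.4%, Aalen-Johansen 48.3%, and one minus Kaplan-Meier with deaths censored 81.2%.

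**Effect of missed deaths.** Protocol 9.9 says that mortality data may capture only 80% of deaths. Take *a* = 0.08 and *d* = 0.04 per month for illustration, with missed deaths as the only censoring. The true and raw 2L shares are both 0.08/0.12 = 66.7%. Aalen-Johansen would tend to 0.08/(0.08 + 0.032) = 71.4%, and for 3L to 51.0% against 44.4%.

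**The case against.** The tables do respect the censoring date in one sense: lines are counted up to it, and the variable is defined as lines reported. No passage claims eventual uptake, and a patient who dies before 2L is correctly a No. A reader might infer that the percentages are simply wrong. The documents do not support that, because as observed counts they are valid.

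The Kaplan-Meier analyses of time to next treatment handle censoring for the same transitions, and SAP 10 promises event and censoring counts for time-to-event variables. This helps but does not settle the matter. Those outcomes are exploratory, and the Table 7 shell shows medians rather than the share reaching a line. The visible text also does not say how death before the next line is treated. If deaths are censored there, a reader who takes uptake off those curves may err further than with raw counts, as the 81.2% shows.

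Cohort 1 has at least 12 months of potential follow-up against a background progression-free survival of 2 to 4 months, so few patients should still be on 1L at study end. This stands: for 2L in Cohort 1, loss to follow-up is the main source.

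No displayed shell breaks lines down by index year, year of diagnosis is an optional subgroup, and nothing ranks the 2L or 3L share as the main result of the secondary objective. The SAP's exploratory, subgroup and sensitivity text is not visible, so further handling there cannot be excluded.

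Missed deaths also stand as an objection. Where censoring is really an unrecorded death, the raw share is not too low and the competing-risk estimate is too high.

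**Conclusion.** The point holds in a limited form. A censoring date is set, the treatment-pattern tables do not separate censored patients from those who died, and the raw percentages therefore understate eventual 2L and 3L use to the extent that patients are lost alive or cut off. With 20% OS censoring, all of it true loss, the shortfall is about 3 to 6 points for 2L and 5 to 7 for 3L. It is greater in late index years and in Cohort 2. These sizes rest on constant hazards, on progression-free survival standing in for time on a line, and on loss unrelated to the next-line hazard. The documents give no line uptake.

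A reader might apply the protocol's 20% to each line, so that a true 66.7% becomes 0.8 × 66.7% = 53.3% and a true 44.4% becomes 0.64 × 44.4% = 28.4%. The documents do not support this, because the 20% is an OS censor rate and not a share of exits from one line. With *a* = 0.08 and *d* = 0.04, that reading needs *c* = 0.03, which is 0.03/0.07 = 43% OS censoring. At 20%, *c* = 0.01, the 2L share is 0.08/0.13 = 61.5% and the 3L share is 37.9%.

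**What to change.** - Keep the raw counts, and label Tables 5 and 6 as lines observed during follow-up.
- In Table 6, split Treated No under 2L and 3L into died without the next line and alive or censored at the last activity date. State the denominator.
- Add the Aalen-Johansen cumulative incidence of starting 2L (from 1L start) and 3L (from 2L start), with death as a competing event, at fixed times such as 6, 12 and 24 months where follow-up allows. Cohort 2 has at most 12 months after 1L start.
- State that capture of about 80% of deaths turns missed deaths into censorings, so this estimate may be too high and should be read beside the raw share.
- Do not restrict the Table 5 mean and median to patients followed to death, which would select short survivors. Under the constant-hazard model it would also correct nothing. With *a* = 0.08, *d* = 0.04 and *c* = 0.01 on every line, the true mean is 1/(1 − 0.667) = 3.0 lines and the raw mean is 1/(1 − 0.615) = 2.6. The mean among deaths is also 2.6, because how a patient exits does not depend on the number of lines.

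The cost is some SAP wording, a few table rows from dates already derived, and one more caveat.
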